To date, no comprehensive, rigorously evaluated primary prevention programs for CSEC exist. Although a handful of programs have been developed to prevent CSEC, they are often awareness-based only programs (rather than skills-based programs), target select groups of youth (e.g., system-involved), seek to prevent revictimization (rather than initial perpetration) or focus on reducing victimization risk only (rather than focusing on perpetrators and/or bystanders), and are rarely (and never rigorously) evaluated. Experts have suggested that CSEC programming focus on healthy and unhealthy relationships, provide youth with general information about sex trafficking, factors related to sex trafficking, and identification of safe people and needed resources. Additionally, programs that include bystander intervention training as well as promoting social norms that protect against violence may help to reduce the incidence of CSEC. Further school personnel are likely critical partners in the prevention of CSEC.

The READY to Stand (RTS) Curriculum (which stands for Report anything dangerous; End the communication; Ask for help; Dont engage; and Your safety first) is a commercial sex trafficking prevention program created for 3rd to 12th grade students and includes programming for school personnel. The RTS for high school students provides students four, 45-minute modules with psychoeducation on CSEC, healthy relationship skills training, identification of safe people and resources, and programming components to enhance valuing of self and others. The RTS will be enhanced with two additional 45-minute modules that focus on bystander intervention training in situations of CSEC and shifting school and community norms to be intolerant of all forms of violence, including CSEC and glamorization of pimp culture.

*** 3. Describe the data collection procedures sequentially. (Upload all interview questions, measurements, images, examples, etc. on page nine. Do not just provide a list of procedures, but rather this section must include enough information for the IRB to understand what the participants will be asked to complete.)**

For this phase of the research project (Component A, Phase I: Refinement and Planning), will we collect focus group data from

youth (n = 80 or until saturation is reached) and school personnel (n=60 or until saturation is reached), and cognitive interview data from youth (n=20).

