ClinicalTrials.gov Data Entry Cover Sheet

Protocol ID: 22811 **Clinical Trials.gov ID:** NCT05988398

Project Title: Preventing Commercial Sexual Exploitation of Children (Project LIVE)

Principal Investigator: [name], University of Nebraska-Lincoln

Statistical Design and Power

Power Analyses

Aim 1a. N/A

Aim 1b. There is no “magic bullet” for sample size in qualitative research.¹²⁷⁻¹²⁹ The sample size proposed for focus groups is consistent with other research conducted by the PI and Co-I ([name]) that should allow for saturation (i.e., the collection of new data does not produce additional insights).¹³⁰ However, the sample size may be adjusted until data saturation is achieved.¹³⁰

Aim 1c. N/A

Aim 1d. Power analyses to support the sample size for the measurement development study (for multi-item measures) are based on prior simulation work.¹³¹ The proposed sample size of $n=878$ baseline surveys from youth will be utilized by splitting the sample in half to conduct exploratory factor analysis (EFA) and confirmatory factor analysis (CFA), each with 439 youth. A sample size of 439 youth is adequate for implementing factor analyses using structural equation modeling approaches and provides power ($> .80$) to estimate two factor models, five manifest indicators each, nonnormal data, and factor loadings = .80.

Aim 1e. Regarding qualitative data, see narrative above for Aim 1b. Also, power analyses were not conducted for descriptive data (e.g., frequencies of the number of sessions attended, extent to which sessions were delivered with fidelity). Regarding student survey data collected as part of the OPT, we will examine changes in intermediary outcomes (see Figure 1) over time given that there will likely not be a sufficient window of time to see changes in behavioral primary and secondary outcomes at the immediate post-test which will happen within a few days to a week or two following the ending of the programming. For the exploratory program impact analysis on intermediary outcomes (Figure 1), a sample size of $n=878$ (approximately .5 assignment rate to condition), will provide adequate power (.80; $\alpha=.05$) to detect a minimum effect size (MDES) $d=.20$ as determined by G-Power analysis of covariance (ANCOVA) routine.

Aim 1f. N/A

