Aim 2a. Power analyses to support the sample size for the effectiveness analyses for our primary, secondary, and intermediary outcomes (see Figure 1) were conducted using G-Power 3.1. Power was set to .80 and $\alpha=.05$. Component A of the study will provide incidence rates which will be used to recalculate power prior to the implementation of Component B. For the purposes of this proposal, we calculated the MDES based on the proposed sample size. For the primary outcome of CSEC perpetration, there are no reliable incidence estimates in the literature on which to draw. With a sample size of 7,241 students enrolled, assuming conservative minimum incidence rates of CSEC perpetration of 1% to 5% (although we hypothesize it will be higher), we have power to detect an MDES difference between conditions, odds ratio (OR)=.49 to .75, respectively. Similarly, for secondary outcomes of CSEC victimization, we estimated a range of incidence rates from a conservation 5% to 50%+ based on literature discussed following for other types of victimization^{96, 132, 133} as well as rates of CSEC youth at increased risk (e.g., system involved, homeless)¹⁸⁻²⁰, which will be present in our sample based on DMPS data, we have the power to detect an MDES difference between conditions, odds ratio (OR)=.75 to .88, respectively. For secondary outcomes of TDV/SV perpetration and victimization, given past 12- months incidence rates¹³² (from nationally representative data from youth) of 63% for perpetration (of any type of TDV) and 69% for victimization (of any type of TDV), we have power to detect an MDES difference between conditions, odds ratio (OR)=.88 to .89. For sub-types of TDV (past 12-month incidence rates: physical victimization: 18%; sexual victimization: 18%; psychological victimization: 66%; physical perpetration: 12%; sexual perpetration: 12%; psychological perpetration: 62%)¹³², we have power to detect an MDES difference between conditions, odds ratio (OR)=.83 to .89, respectively. For the secondary outcome CSEC bystander action and opportunity and intermediary outcomes (i.e., knowledge, valuing of self and others, healthy relationship skills, bystander efficacy, perceptions of school social norms, prevention conversations with school personnel), the ANCOVA routine suggested power (.80) to detect a small difference between groups (MDES $d=.06$).

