Aim 1d. Rigorous psychometric evidence for the newly developed multi-item measures will be evaluated using multiple indices (as most applicable to each measure) as guided by the American Educational Research Association standards⁹². First, using data from the baseline (pretest), we will randomly assign students to either Phase 1 (EFA; $n=435$) or Phase 2 (CFA; $n=435$) to determine evidence of internal measurement structure. In Phase 1, we will examine the factor structure by conducting EFA using the common factor model and full information maximum likelihood (FIML) estimation with oblique rotation within a structural equation modeling (SEM) framework¹⁴⁰ in Mplus¹⁴¹. This rigorous method retains all cases with the assumption that any missing responses are missing at random (MAR) to maintain power and improve estimation under conditions of missing data¹⁴². We will employ parallel analysis to determine the appropriate number of factors¹⁴⁰ (and then evaluate the fit of the model within SEM)¹⁴⁰. After conducting the EFA, we will then replicate the measurement structure in a new sample of students using CFA within SEM with FIML. We will also examine internal consistency estimates of reliability of our measures. Next, we will examine evidence of convergent associations between the newly developed measures with existing, psychometrically sound measures (see Table 3). Structural regression models will be estimated including a latent and manifest measurement model and regression paths to determine associations between the newly developed multi-item and single-item measures and existing measures to determine if associations are in the theoretically derived hypothesized

direction. Model fit will be determined using multiple indices, including chi-square statistic, root mean square error of approximation (RMSEA ≤ 0.08), the comparative fit index (CFI ≥ 0.90), and the standardized root mean square residual (SRMR ≤ 0.10)¹⁴³.

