We will test the hypotheses related to examining effectiveness of participation in the RTS in leading to reductions in CSEC perpetration (primary outcome), as well as reductions in CSEC victimization and TDV and SV victimization and perpetration and increases in bystander intervention in CSEC situations (secondary outcomes). To improve the rigor of analyses for Aim 2a, we will use propensity-score analysis to reduce the impact of selection bias, and latent constructs, when possible, to reduce measurement error, reduce paths and variables, and increase statistical power (MacCallum et al., 1996). This approach produces rigorous estimates of causal effects within the context of quasi-experimental designs when random assignment is not possible by controlling confounders, including selection effects¹⁴⁴. This approach will use four analytic steps: (1) estimate propensity scores in a separate analysis, (2) use the propensity scores to adjust for confounding, (3) assess balance, and (4) estimate the propensity score-adjusted treatment effects (Lanza et al., 2013). In step 1, to estimate the propensity score, we will consider all pertinent confounders and covariates (see Measurement Table 3). This step will use logistic regression of condition on the potential confounders to obtain each student's propensity score. All measured confounders that are predictive of selection into the experimental conditions and the outcomes will be included in the propensity model. Standardized mean differences in covariate values across treatment and comparison conditions will be used to determine the final set of confounders to include in estimating the propensity score. In step 2, an initial treatment effect model is estimated that adjusts for confounding using the propensity score. We will use inverse probability weighting (IPTW) to adjust for confounding. The standardized mean differences between experimental groups are computed on the weighted sample included the IPTW-adjusted propensity score (Step 2). If IPTW does not provide optimal balance, then other methods will be considered (e.g., matching). Then Step 3 is used to determine balance on the potential confounders included in the propensity score across the experimental groups. The goal is to determine whether there are any differences remaining on the confounders between experimental groups (balance = standardized mean differences $< |0.2|$ after adjustment). Confounders will be adjusted and the propensity score model (Step 1) will be re-estimated until balance is reached. Once balance is determined, the outcome analysis will be conducted in Step 4 via SEM. The experimental effect of interest will be the Average Treatment Effect (ATE), which is the population-level average effect of condition on the primary and secondary outcomes as detailed in the logic model. The effects of interest quantified are differences between experimental conditions at post-test and follow-up on outcomes (for continuous measures), the propensity score as a covariate. These effects indicate whether the outcomes in the experimental condition differ significantly from those in the comparison condition. At post-test and follow-up, we expect the difference between the experimental conditions to be significantly greater than zero, reflecting better outcomes for those in the RTS program as compared to those in the wait-list condition, after adjusting for the

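### The plan never checks that multi-item outcomes measure the same thing in both arms after RTS, so a shift in how items work could pass for, or hide, an effect on the latent outcomes

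*SAP*

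**What the plan says.** **Validation.** In the SAP (Proposed Analyses, Aim 1d), the structure of the new multi-item measures is examined once: "using data from the baseline (pretest), we will randomly assign students" to an exploratory or a confirmatory factor analysis half. Reliability and convergent associations are also to be examined, with no time point given. The cognitive interviews (Protocol, Purpose, Methods & Procedures, item 3) check comprehension while the survey is still being built, before any trial student has had RTS.

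**Comparison.** Aim 2a combines propensity scores with latent variables: "and latent constructs, when possible, to reduce measurement error". Differences between arms at post-test and follow-up are estimated by SEM in Step 4. Categorical outcomes go to logistic regression. Step 4 models are judged on chi-square, RMSEA (.08), SRMR (.10) and CFI (.90). The multiple-group models of Aim 2b concern demographic moderators and constrain structural paths only.

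**Programme content.** The Protocol (same section, item 2) says the high-school curriculum has "four, 45-minute modules with psychoeducation on CSEC, healthy relationship skills training, identification of safe people and resources", plus material on valuing self and others. Two further modules will cover bystander action and norms.

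**Power.** The SAP (Power Analyses, Aim 2a) gives a detectable d of .06, introduced by "For the secondary outcome CSEC bystander action and opportunity and intermediary outcomes".

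Neither document plans a test of measurement invariance or differential item functioning by arm or by time.

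**The concern.** A difference in latent means between arms is interpretable only if the items relate to the construct in the same way in both arms. RTS students are taught what CSEC is, how to recognise it and what norms to hold; wait-list students are not. After the programme, an RTS student might answer an item on bystander opportunity or school norms differently because the item now means something else to that student, and not because opportunity or norms changed. A factor structure established before exposure says nothing about this. Propensity weighting cannot remove it either, because it balances confounders of assignment and the shift arises after assignment.

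The stakes come from scale. A trial planned to detect d = .06 is sensitive to artefacts of that size. An artefact could produce a false effect on a bystander or intermediary outcome, hide a real one, or enter the Aim 2b mediation models as an apparent path through a mediator.

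**Working it through.** **Inputs**
- N: "With a sample size of 7,241 students enrolled" (SAP, Power Analyses, Aim 2a).
- Allocation: 1:1 is assumed. The only stated figure, "approximately .5 assignment rate to condition", is for the open pilot (Aim 1e).
- Power .80 and alpha .05 (Aim 2a); sidedness is not stated.
- Five indicators per factor, loadings .80 (Power Analyses, Aim 1d), so residual variance is 1 − .64 = .36.
- The item shifts in the RTS arm and the design effects are assumptions. The true effect is set to zero.

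**1. The plan's own figure.** MDES = (z for alpha + z for power) / √(N/4), with √(7241/4) = 42.55.
- One-sided: (1.645 + 0.842)/42.55 = .058.
- Two-sided: (1.960 + 0.842)/42.55 = .066. With a covariate explaining 17% of variance, .066 × √.83 = .060.

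The stated .06 is reproduced under either reading.

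**2. Spurious latent difference.** With equal loadings, d ≈ (sum of item shifts / 5) / .80.
- 0.25 SD in one item: .05/.80 = .0625.
- 0.3 SD in one item: .06/.80 = .075.
- 0.20 SD in two items: .08/.80 = .100.

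**3. Would the fit limits notice?** A one-factor model with condition as predictor was fitted by maximum likelihood to the population covariance matrix, omitting the item-by-condition effect (9 df):

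| Shift in RTS arm | Spurious d | RMSEA | SRMR | CFI |
|---|---|---|---|---|
| 0.25 SD, one item | .061 | .062 | .024 | .988 |
| 0.3 SD, one item | .072 | .074 | .029 | .983 |
| 0.20 SD, two items | .100 | .061 | .024 | .988 |
| 0.05 SD, all five items | .0625 | 0 | 0 | 1 |

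All four exceed .06 and pass RMSEA .08, SRMR .10 and CFI .90. The .072 and .100 also exceed the two-sided .066.

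**4. Chi-square.** Noncentrality = N × df × RMSEA². For 0.3 SD in one item, 7241 × 9 × .0737² ≈ 354 on 9 df, so rejection is practically certain. For the uniform shift it is 0.

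**5. How often would it be declared significant?** Take the five-item composite with a 0.3 SD shift in one item.
- Composite SD = √((25 × .64 + 5 × .36)/25) = √.712 = .844.
- d = (0.3/5)/.844 = .071, and the expected z is .071 × 42.55 ≈ 3.03.
- Two-sided .05, no clustering: rejected about 86% of the time.
- Design effect 1.5: z = 3.03/√1.5 = 2.47, about 70%.
- Design effect 3: z = 3.03/√3 = 1.75, about 42%.

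The nominal rate is 5%.

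**The case against.** **The primary outcome is outside the mechanism.** This stands. CSEC perpetration is powered as an incidence of 1% to 5%, CSEC victimisation and TDV/SV are also powered as incidences, and categorical variables go to logistic regression. Latent variables are used only where possible. A reader might infer that the primary result itself is compromised by latent scoring; the documents do not support that. Reporting change could bias a binary outcome, but by a different route.

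**Chi-square would react.** This stands for one- or two-item shifts (step 4), and a larger one-item shift of 0.35 SD would breach the RMSEA limit (.086). But the SAP gives chi-square no decision rule or follow-up action. An overall rejection also does not say whether the misfit has anything to do with arm.

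**Nothing shows that a shift will occur.** Also correct. A reader might infer that every outcome is an unblinded self-report and that a shift will be counted as a programme effect. The Protocol speaks of surveys and the SAP of a wait-list, so self-report and awareness of condition are reasonable inferences, but they are not stated for every outcome. The table of measures and the instruments are not available here. Direction is also open: better recognition could raise reports and hide a benefit, while norm messages could do the opposite.

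**Existing measures and earlier safeguards.** The SAP calls its existing measures psychometrically sound, and the cognitive interviews and pilot refine the survey. These help with item quality. They do not show that items work alike in trained and untrained students.

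**Invariance tests miss a uniform shift.** True, as the last row of the table shows. The step is therefore a partial safeguard and must be described as one.

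**Conclusion.** The gap is real but bounded. The structure of the new multi-item measures is established before exposure, arms are compared on latent constructs after exposure, and nothing in between checks comparability by arm or time. It matters for outcomes and mediators that will be latent or multi-item: probably bystander action, the intermediary outcomes and the Aim 2b mediators.

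Under the assumed shifts, the spurious d is .061 to .100 against a stated detectable .06, within the RMSEA, SRMR and CFI limits. For the 0.3 SD one-item shift, false rejection is about 86% without clustering. It is about 42% to 70% at design effects of 3 to 1.5, which is the fairer range because the SAP itself adjusts for classroom.

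These figures rest on 1:1 allocation, all 7,241 students analysed, item SDs near 1, no covariate gain in the rejection rates, and shift sizes that the documents neither give nor rule out. They show that the plan could not separate response shift from change. They do not show that response shift will happen, or in which direction.

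**What to change.** Add to the SAP, before Step 4 of Aim 2a and before the Aim 2b mediation models:

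1. For each multi-item outcome and mediator, test configural, metric and scalar invariance (thresholds for categorical items) across condition at post-test and at follow-up, and across time within condition. State the decision rule in advance.
2. Where scalar invariance fails, free the affected items, estimate the arm difference under partial invariance, and report it beside the unadjusted estimate.
3. State as a limitation that a shift common to all items, or a reporting change in a binary outcome, is not detected by this step and could bias results in either direction.
4. Optionally, repeat at follow-up one item about a fixed pre-programme period and compare by arm how often baseline answers change. Use this descriptively only. It should not be a correction factor for the primary odds ratio: that would assume the same reporting change for past and current behaviour, and at 1% prevalence only about 36 students per arm (.01 × 3,620) would report the behaviour.

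The cost is additional SEM runs in Mplus, which the SAP already names, on data already planned, and slightly less precision under partial invariance. The optional item must be in the survey before data collection starts.

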*** 16. Does this project involve a FDA-approved and marketed device and it is NOT the object of the investigation?**

No

Purpose, Methods & Procedures

1. Indicate the project's design by checking the appropriate box(es):

 Action research	 Case-control
 Class Project	 Cohort
 Correlational	 Cross-sectional
 Ethnography	 Exploratory
 Evaluation	 Intervention
 Longitudinal	 Pilot
 Randomized	 Other

*** 2. What is the significance/purpose of the project? (Provide a brief description in lay terms including a brief literature justification and objectives/aims of the research.)**

The overall goal of the 5-year project is to conduct both a process and rigorous outcome evaluation of The Set Me Free Projects (SMFP) READY to Stand (RTS) curriculum with an eye toward widespread dissemination to other U.S. communities, if deemed effective.

The overall project is divided into Components A and B, and three different IRB Phases for IRB approval as follows:

1. Component A, Phase I: Focus groups with students (n = 80) and school personnel (n = 60); cognitive interviews with students (n = 20)

2. Component A, Phase II (Open Pilot Trial/OPT): Survey data from students (n = 878) and school personnel (n = 78) to further refine the surveys and procedures; and

3. Component B, Phase III (RCT): quasi experimental study

The current application is for Component A, Phase 1 aimed at planning and refinement of instruments through FG and cognitive interview data.

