
propensity score. For categorical variables, logistic regression will be used to examine differences in prevalence by condition. The experimental condition is the independent variable in these models. Multilevel modeling is not possible given the small number of schools; thus, school will be included as a covariate. Classroom will be used as a cluster variable to adjust the standard errors for nesting. Models for Step 4 will be evaluated for overall model fit via χ^2 statistic, RMSEA :s .08, SRMR :s .10, and CFI \geq .90. We will evaluate our hypotheses across several indicators, including significance (p), confidence intervals, and the standardized difference between groups (d), as well as the directionality of included path coefficients, and odds ratios.

Mediation and Moderation Analyses (Aim 2b).

We will assess mediators (e.g., perceptions of norms intolerant of CSEC) and demographic moderators (e.g., gender) of program effectiveness, including the propensity score and school as covariates in all models. To test for mediation, we used the product of coefficients method using bias-corrected bootstrapping with 1000 resamples to calculate the confidence intervals¹⁴⁵ (MacKinnon, 2012). For our moderators (e.g., age, gender, racial groups, sexual orientation), we will estimate structural equation multiple group models, first allowing estimation of the path coefficients to vary freely across groups, and then constraining paths to be equal when a structural path coefficient of interest was significant for one group and not the other group. We will conduct model comparisons using the chi-square (χ^2) difference test (i.e., χ^2 , $p < .05$ indicating moderation).

Aim 2c. Descriptive statistics will be used to examine the extent to which sessions were delivered with fidelity. Process observations will be analyzed using thematic analysis as described above for Aim 1b.

Aim 2d. Descriptive statistics will be used to examine the frequency of responses to close-ended questions (e.g., To what extend did you like the session today?). Open-ended questions will be analyzed using thematic analysis as described above for Aim 1b.

Aim 2e. Interview data will be analyzed using thematic analysis as described above for Aim 1b.

Aim 2f. The purpose of this aim is to determine costs associated with the program implementation to inform future economic evaluation of the RTS. The process for documenting costs are described in Section C.18.

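### If RTS is assigned by classroom, differences between classrooms can pass the planned propensity weighting and balance check; the SAP should state the unit of assignment and add classroom-level covariates and checks

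*SAP*

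**What the plan says.** The protocol (Purpose, Methods & Procedures, item 2) lists the main evaluation as "Component B, Phase III (RCT): quasi experimental study". The SAP (Outcome Analyses, Aim 2a) treats it as non-randomised and adopts propensity scores to obtain causal estimates "within the context of quasi-experimental designs when random assignment is not possible by controlling confounders, including selection effects".

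- **Step 1.** For the propensity model, "we will consider all pertinent confounders and covariates (see Measurement Table 3". Measured confounders that predict both selection and outcome go in. "This step will use logistic regression of condition on the potential confounders to obtain each" student's score.
- **Step 2.** Inverse probability weighting is applied.
- **Step 3.** "The goal is to determine whether there are any differences remaining on the confounders between experimental groups"; balance means an absolute standardized mean difference (SMD) below 0.2.
- **Step 4.** The outcome model estimates the average treatment effect (ATE). School is a covariate because there are too few schools for a multilevel model. "Classroom will be used as a cluster variable to adjust the standard errors for nesting".

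Neither document names a classroom-level covariate (grade, course, teacher, classroom average at baseline) or a classroom-level balance check. Neither states the unit of assignment. On delivery, the protocol says "The RTS for high school students provides students four, 45-minute modules", with two more modules to be added.

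**The concern.** If whole classrooms receive RTS or wait for it, selection acts on classrooms. A student's own baseline answers say little about the class the student sits in. Weighting on those answers can therefore make the students look alike while RTS classrooms still have higher or lower average risk than wait-list classrooms.

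That matters if class-level risk predicts later outcomes beyond the student's own baseline report. It may do so through peers, or because self-reports are unreliable and the class average carries extra information. The difference left behind then appears as a programme effect. Clustering the standard errors by classroom changes the precision claimed, not the bias. The school covariate removes additive differences between schools, not between classrooms within a school. The Step 3 check, as described, would not reveal the problem.

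**Working it through.** **1. At what level does condition vary?** If whole schools were assigned, school indicators would absorb condition and Step 4 could not estimate its effect. The planned model therefore needs variation within schools. Classroom is the declared cluster, and RTS is taught in sessions. Classroom-level assignment is a strong inference, but not a stated fact.

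**2. The yardstick.** SAP, Power Analyses, Aim 2a gives a minimum detectable effect (MDES) of d = .06 for bystander and intermediary outcomes, with N = 7,241, power .80 and alpha .05. With 1:1 allocation and independent students, MDES = (z_alpha + z_power) × 2/√N:

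- one-sided: (1.645 + 0.842) × 2/85.09 = .058
- two-sided: (1.960 + 0.842) × 2/85.09 = .066

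The stated figure reproduces one-sided. It serves here only to judge the size of a bias.

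**3. Why student balance does not show classroom balance.** When selection follows the class component of a confounder, student SMD ≈ class SMD × √ICC. Take a class SMD of about .49, which is what selection at log-odds .5 per SD produced on a classroom variable in the simulation below:

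- ICC .05: .49 × .224 = .11
- ICC .10: .49 × .316 = .15

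The simulated unweighted student SMDs were .10 and .15. Both are under the 0.2 limit before any weighting.

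**4. Simulation with an error-free baseline.** All inputs are assumed; none is in the documents. There were 290 classrooms of 25 in 8 schools, confounder ICC .05 or .10, no programme effect, and 200 replicates. School was in both the propensity and outcome models, and the outcome model also included the propensity score. The classroom mean's own effect was 0 or .10, and a separate classroom variable explained about 2% of outcome variance. After student-level weighting the student SMD was 0.00 in every row. Ranges cover the two ICCs.

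| Selection (log-odds per SD) | Own effect of class mean | Class-mean SMD after weighting | False d, student values only | False d, class means added | False d, class variable also added |
|---|---|---|---|---|---|
| None | .10 | .00 | .00 | .00 | .00 |
| Class mean, .5 | 0 | .34–.36 | .00–.005 | .00–.004 | .00 |
| Class mean, .5 | .10 | .33–.36 | .046 | .016–.021 | .014–.019 |
| Class variable, .5 | 0 | .00–.01 | .068–.072 | .068–.072 | .00 |
| Both, .25 | .10 | .18–.19 | .057–.058 | .041–.045 | .006–.008 |
| Both, .5 | .10 | .31–.35 | .107 | .079–.085 | .015–.021 |

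In the last three rows the class variable itself kept an SMD of .24–.49 until it was modelled.

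**5. Simulation with an imperfect baseline.** Also assumed: 329 classrooms of 22, reliability .8, ICC .05–.10, selection log-odds .5–1.0, class effect 0–.10. Student SMD was 0.00, classroom-mean SMD about .3–.6 and false d about .01–.11. Two settings, tested two-sided at .05:

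- ICC .05, selection .5, class effect .05: bias .030, false-positive rate 25%. With classroom means: bias .020, rate 16%.
- ICC .10, selection 1.0, class effect .10: bias .107, rate 100%. With classroom means: bias .040, rate 40%.

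Across settings, classroom means cut the bias by about 40%–60% in most cases; these two give 1 − .020/.030 = 33% and 1 − .040/.107 = 63%. With no class selection, or an error-free baseline and no class effect, bias was about 0 and rejection 5%–6%.

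**6. Binary outcome near 5%** (class log-odds .1–.2). The false odds ratio was 1.05–1.21 and the false-positive rate 8%–38%, falling to 4%–19% with classroom means. The SAP's MDES at 5% is OR .75, so |ln .75| = .288. Then ln 1.05/.288 = .049/.288 = 17%, and ln 1.21/.288 = .191/.288 = 66%. Incidence of 1% was not simulated.

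**The case against.** A reader might infer that the scores use nothing but each student's own values, that RTS certainly goes to whole classrooms, and that the ATE is therefore biased. The documents do not support that reading. A score for each student says who receives a score, not at what level the predictors are measured. Table 3 is not in the supplied text, and the Step 1 entry rule would not exclude classroom variables. The unit of assignment has to be inferred. Nothing says that classrooms are chosen on risk.

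The sizes also rest on assumed inputs, and the wide range of false-positive rates reflects those inputs. The .06 yardstick does not apply to the primary outcome, where the simulated bias stays below the MDES. The planned use of latent constructs might reduce the measurement-error route, though the SAP says only where possible and does not extend it to Step 1. Finally, adding classroom means leaves bias behind, so a classroom-level check could also pass while some bias remains.

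All of this stands as a limit on the claim. What it does not answer is that the text commits to no classroom-level covariate or check. An instruction to include measured confounders does not by itself produce classroom averages of the baseline outcomes.

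**Conclusion.** The point holds in conditional form. If condition varies by classroom within school, and selection into RTS is related to classroom risk, differences between RTS and wait-list classrooms can survive the planned weighting, pass Step 3 and bias the ATE. Under the assumed inputs the false effect is about d = .01 to .11, so at the upper end it exceeds the .06 that the SAP sets out to detect for bystander and intermediary outcomes. For a binary outcome near 5%, it is about one sixth to two thirds of the detectable log odds ratio.

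The direction follows the direction of selection. The odds ratios above 1 come from a scenario that makes RTS look harmful; selection the other way would flatter it. The bias is about nil without such selection, or if baseline is error-free and there is no class effect. The figures show order of magnitude only. This is a cheap improvement to the plan, not a demonstrated error in it.

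**What to change.** 1. State the unit of assignment in Component B.
2. If it is the classroom, add to the Step 1 propensity model the classroom means of the baseline outcomes and main confounders, beside each student's own values, plus any other measured classroom features such as grade or course. Say which of these Table 3 already contains. The extra features matter: where an unmodelled classroom variable also drove selection at .5, classroom means alone lowered the false effect only from .107 to .079–.085.
3. In Step 3, require and report balance on these classroom-level values as well as on student values.
4. State residual classroom-level confounding as a limitation, since the change reduces the bias without removing it.

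The cost is SAP wording. The classroom means come from baseline data already planned. Weights become slightly more variable: the SD of the estimate rose from about .026 to .028 in the worst simulated settings.
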